Clinical Trials Unit	
Pragmatic Clinical Trials Unit (PCTU) Centre for Primary Care and Public Health Blizard Institute [name] [contact]

Key Protocol Contributors	
[name] [name] [name] Unit for Social and Community Psychiatry Newham Centre for Mental Health

	
[name] [contact] Emails: [contact]; [contact]; [contact]

Statistician	
[name] Pragmatic Clinical Trials Unit (PCTU) Centre for Primary Care and Public Health Blizard Institute [name] [contact] Email: [contact]

Committees	
Programme Management Group (co-applicants), Lived Experience Advisory Group

STUDY SUMMARY

Study Title	Assessing social contacts and social activities of people with psychosis
Internal ref. no. (or short title)	SCENE (WP1)
Study Design	Mixed methods cross-sectional survey
Study Participants	Patients with a diagnosis of a psychosis-related condition (ICD10 F20-29); aged 18-65; receiving care from outpatient secondary mental health services or in primary care; capacity to provide informed consent; ability to communicate in English
Planned Sample Size	500 patients
Study duration	Month 1-13
Planned Study Period	1 st of June 2017-30 th of June 2018
Study aims and objectives	
Aim: To assess social contacts, activities and wishes to expand social networks of people with psychosis
 
Objectives:
 
 1. Assessing wishes of people with psychosis for expanding their social networks in order to estimate recruitment rates for a future clinical trial. 2. Assessing social contacts and social activities of people with psychosis 3. Identifying patient-level characteristics associated with social contacts and social activities

FUNDING AND SUPPORT IN KIND

FUNDER(S) (Names and contact details of ALL organisations providing funding and/or support in kind for this trial)	FINANCIAL AND NON FINANCIAL SUPPORT GIVEN
National Institute for Health Research	Programme Grant for Applied Research
East London NHS Foundation Trust (supported by Noclor)	Study sponsorship
East London NHS Foundation Trust	NHS support costs. Permission to conduct study on Trust premises with Trust employees and service users
Tees, Esk & Wear Valleys NHS Foundation Trust	NHS support costs. Permission to conduct study on Trust premises with Trust employees and service users
Devon Partnership NHS Trust	NHS support costs. Permission to conduct study on Trust premises with Trust employees and service users
Queen Mary University of London	Substantive employer of Chief Investigator

ROLE OF STUDY SPONSOR AND FUNDER

East London NHS Foundation Trust the sponsor, Noclora Research Support Service is acting on behalf of East London NHS Foundation Trust to assume overall responsibility for the initiation and management of the study. The National Institute of Health Research has provided funding for the study.

ROLES AND RESPONSIBILITIES OF TRIAL MANAGEMENT COMMITTEES/GROUPS & INDIVIDUALS

Study Management Committees

The main roles and responsibilities of each committee are outlined below:

- Programme Management Group

The Programme Management Group (TMG) includes the PI, 10 co-applicants, the main researchers and patient representatives from the Lived Experience Advisory Panel. The PMG will meet regularly to ensure all practical details of the study are progressing well and working well and everyone within the trial understands them. The PMG will meet every two to three months initially, and at least three times per year throughout. The project timeline and milestones will be scrutinised at each meeting. More regular and individual meetings between the PIs, the co-applicants and the different parts of the research team will be arranged, including Skype video and teleconferencing, as appropriate.

- Lived Experience Advisory Panel

IDMC	Independent Data Monitoring Committee
ISF	Investigator Site File
ISRCTN	International Standard Randomised Controlled Trials Number
NHS R&D	National Health Service Research & Development
NIMP	Non-Investigational Medicinal Product
PI	Principal Investigator
PIC	Participant Identification Centre
PIS	Participant Information Sheet
PMG	Programme Management Group
QP	Qualified Person
RCT	Randomised Control Trial
REC	Research Ethics Committee
SAE	Serious Adverse Event
SDV	Source Data Verification
SOP	Standard Operating Procedure
SSI	Site Specific Information

STUDY FLOW CHART

Please see Appendix 1 for schedule of events.

Flow chart for Work Package 1 survey:

STUDY PROTOCOL

Assessing social contacts of people with psychosis

1 BACKGROUND

About 120,000 people with psychosis are being cared for in secondary services in the NHS at any point in time. Reviews show that people with psychosis have much smaller social networks compared with the general population and other groups with long-term mental and physical disorders (Emlet 2006); and more than 50% of their reduced social networks consist of family members rather than friends and other contacts (Palumbo et al. 2015).

Social isolation is usually understood as a lack of sufficiently large and supportive social networks, with few friends and limited social contacts. In an analysis of data of 1396 patients with psychosis from four international multi-centre studies ([name] et al., 2012), 45% were found not to have met any friend in the previous week. In a recent survey in East London ([name] et al., 2016), 80% of patients with psychosis felt lonely, and 43% very or extremely lonely. Only 30% had had more than one social contact in the previous week. Furthermore, research has shown that smaller networks with loneliness, the absence of reliable social contacts and lower social support predict poorer quality of life and unfavourable health outcomes in patients with psychosis (Cohen et al, 1998; Clinton et al, 1998; Bengsson-Tops and Hansson, 2001; Norman et al., 2005). A study carried out in Italy has showed that social networks can be expanded with a relatively simple intervention in which mental health professionals help patients to identify their preferences for social activities (Terzian et al., 2013). The overall aim of the NIHR-funded research programme of which this study is part is to adapt this intervention to the NHS and to test whether it expands social networks and improves patients' quality of life.

In this specific study we will aim to obtain more accurate estimates of social contacts and social activities in people with psychosis in different areas of England and to understand how many of them are willing to engage in an intervention to expand their social networks.

2 RATIONALE

Available research suggests that many patients with psychosis tend to be highly socially isolated ([name] et al., 2016) and those who are socially isolated have a worse quality of life (Becker et al., 1998; Bengsson-Tops et al., 2001).

Previous studies in the UK have focused on urban contexts ([name] et al., 2016) and there is a need to explore social contacts of people with psychosis living in different areas. There is evidence that social deprivation and inequality are linked to psychosis (Kirkbride et al., 2014; O'Donoghue et al., 2016), however we do not know how these measures of neighbourhood social composition relate to social isolation in people with psychosis.

Moreover, we also need an indication of how many people with psychosis may be interested and prepared to expand their social networks with the support of mental health staff.

Currently, there are no specific interventions in the UK that focus on expanding social networks for people with psychosis. If NHS services address service users' relationships, they usually focus on

established and close relationships, mainly with the service user's partner or family. However, there are good reasons to focus a new intervention on contacts outside families: a) for many service users, particularly for those who live in social isolation, families are not available and/or the potential for contacts with family members are limited; b) when service users are still in contact with families, the relationships are often well-established with little option for further change; c) services usually have already tried family interventions, if possible, at some stage in the service user's history as they are recommended by NICE guidelines for this patient group; d) family relationships can be difficult and rather stressful for some service users; and e) the reduced social networks of patients with psychosis consist mainly of family members and what is missing are other contacts, that can be more flexibly established and shaped, and that service users can also more easily terminate if they wish to.

We have discussed our plans with 30 people from various service user groups; 29 strongly endorsed the proposal for developing an intervention to expand social networks. One participant said, "This is very relevant. I witness and experience this isolation... I miss being... part of a group".

2.1 Assessment and management of risk

Risks of the project and measures to prevent them

We have identified potential risks related to participation, confidentiality and use and storage of personal data and devised strategies to avert or minimise them.

Participation: There are unlikely to be adverse effects of taking part in the research. However, as social isolation may be a sensitive topic that might be related to broader personal experiences, some participants may find discussing the subject matter in an interview upsetting.

1. Participants will not be asked to share their own personal experiences (although they are free to do so if they wish).
2. Informing patients that they may leave interviews at any time and that they do not have to answer any questions that might make them feel distressed or uncomfortable.
3. Informing patients that the research team are able to contact their clinicians if they would like further support.

Confidentiality: To protect the identification of participants, study IDs will be created and assigned for each individual, and person-identifiable data will be stored separately in a locked filing cabinet at each participating Trust. An electronic file with restricted access (to the core SCENE research team only) will be maintained at each site. Only an ID list (which will not contain any patient identifiable data) will be transferred to the central study team at East London NHS Foundation Trust. A log will document any formal changes to the ID list document.

Where the researcher has concerns regarding the participant's safety or the safety of others, through participant disclosures of thoughts/plans of harming themselves or others, or through criminal disclosures; then the researcher is obliged to break confidentiality and inform the relevant clinical teams, services and/or authorities. This will be made clear to the participant on the information sheet and during the consent process to ensure their understanding.

We will also remind all participants that they do not have to answer any questions or make any personal disclosures if they do not wish to

Use and storage of personal data: All participant data collected will be pseudonymised and handled in line with the Data Protection Act 1998. Data will be handled and stored in accordance with the conditions set out by the study sponsor (East London NHS Foundation Trust). All data handling and management activities delegated to the PCTU will comply with the unit's own procedures and information governance requirements.

Benefits of the project

There are no direct benefits for participants in relation to the study. A potential long-term benefit for all participants taking part in this study is that this survey will help the development of a new intervention to extend the social networks of service users with psychosis in the context of the NHS. Patients who have larger social networks also report higher quality of life compared to those who are socially isolated (Becker et al., 1998; Bengtsson-Tops and Hansson, 2001). Hence, this intervention may improve quality of life of patients with psychosis.

Safety reporting

The study will consist of a survey assessing social contacts. This work package does not involve any treatment or addition to patients' usual care. Adverse Events and the need for Urgent Safety Measures are not anticipated.

Adverse Events (AE)

Any adverse events will be recorded in the study file and the participant's records, if appropriate. The participants will be followed up by the research team.

Serious Adverse Event (SAE)

SAEs that are "related" and "unexpected" will be reported to sponsor within 24 hours and to the main REC within 15 days of learning of the event.

Urgent Safety Measures

In the case of urgent safety measures being required, the CI will inform the sponsor and the REC of the event immediately via telephone. The CI will then inform the REC and the JRMO in writing within 3 days.

Annual Safety Reporting

If required by the REC, the CI will send the Annual Progress Report to the main REC using the NRES template and to the sponsor.

Overview of the Safety Reporting responsibilities

The CI will ensure that safety monitoring and reporting is conducted in accordance with the sponsor's requirements.

3 STUDY DESIGN

Mixed methods cross-sectional survey

4 STUDY SETTING

This multi-centre study is hosted by East London NHS Foundation Trust as coordinating centre, and Tees, Esk & Wear Valleys NHS Foundation Trust and Devon Partnership NHS Trust are the core centres. Other NHS Trusts within urban and suburban areas within England will participate as research sites. Patient participants will be recruited and data collected at these sites.

Participants across all sites will be identified both through secondary care mental health services and through primary care services in the participating NHS trusts.

5 ELIGIBILITY CRITERIA

5.1 Inclusion criteria

- 18-65 years old
- Diagnosis of psychosis-related condition (ICD-10 F20-29)
- Receiving care from outpatient secondary mental health services or in primary care services
- Capacity to provide informed consent
- Ability to communicate in English

5.2 Exclusion criteria

- Does not meet inclusion criteria
- Primary problem of current substance use disorder
- No capacity to provide informed consent
- Hospitalised in the week before the interview (but these participants can be re-approached at a later time)

6 STUDY PROCEDURES

This study will aim to identify the number of social contacts and social activities in people with psychosis and wishes of patients to expand their social network in order to provide background data for the development of a novel intervention to expand patients' social networks.

Consent

Eligible patients will be identified by members of their wider clinical team (not their main treating clinician) and asked for their verbal expression of interest to speak to a researcher before they do so. Informed consent will be sought from eligible patients to participate in this study, which will include permission to access medical records to retrieve clinical socio-demographic and clinical

characteristics. Participants will be given the option during the consent process to receive a copy of the findings from the survey.

Demographic and clinical characteristics data collection

The research team member conducting the survey will ask participants for consent to obtain demographic and clinical characteristics from medical records and record this data in the Survey CRF. We will record postcodes in order to convert them to the Lower-layer Super Output Area (LSOA) that each postcode falls within. Data will be entered into a database developed by the PCTU, held on a secure server.

Survey

The survey will take place in quiet rooms in community mental health teams or in primary care setting, quiet rooms in the University where researchers are employed or at patients' homes and will be conducted as an interview by a research team member who will complete a case report form (CRF) recording patients' responses. The survey will include questions about the number and quality of social contacts on each day of the previous week ([name] et al., 2016), including detailed questions about social activities as developed in the on-going PGfAR VOLUME (on volunteering in mental health) ([name] et al., 2016) and subjective quality of life ([name] et al., 1999). Participants will also be asked about their wishes to expand their networks; their willingness to do so through a targeted intervention over six months, if such an intervention was offered; and their potential willingness to participate in a randomised controlled trial, if asked to. In further open questions, we will then ask for potential reasons for participating or not participating in a trial. This one-off survey will take between 45 minutes to complete.

Payment to participants

Participants will be offered £15 cash or voucher as a reimbursement of their time after completion of the survey.

6.1 Recruitment

Patients will be identified by clinicians and clinical studies officers (CSOs) using medical records where necessary. At this stage, the minimum amount of information will be logged to ascertain eligibility: name, RIO or NHS number, and diagnosis. Addresses will only be logged for randomly selected and eligible patients, so that letters can be sent inviting them to take part.

6.1.1 Patient identification

Patients will be recruited from the caseloads of primary care services or outpatient secondary care mental health teams. Clinicians or CSOs, who are part of the wider clinical team for the patient will screen and identify eligible patients. Depending on the size of teams, all caseloads or a subset of caseloads will be screened. The eligible patients will be invited to take part in the survey by letter. We will also ask clinicians to provide information about the study to patients (face-to-face or by phone). The research team will not contact patients or speak with them directly unless patients have provided a verbal expression of interest to clinicians or a response from letters to do so. If identified patients cannot be interviewed, we will approach other patients randomly selected from the list.

6.2 Consent

All patients who respond to study information with interest will be contacted and invited to attend a face-to-face meeting. Researchers who are independent from clinical teams, will go through information sheets with interested individuals and time taken to answer any questions or concerns that are raised. At this stage, contact details will be confirmed, and availability ascertained for attendance of the survey interview. Participants will be given the option to proceed with the interview immediately or to have up to one week to consider their participation. The option to proceed immediately to interviews is given because of the unlikely harm from the study, consisting in a one-off interview, and weighing the potential burden in terms of time for the patient in case they need to meet the researcher again.

All participants will be asked to provide informed consent, by initialling, signing and dating an informed consent form before any data collection begins. Capacity to consent to research will be ascertained by researchers through a standardised template. Researchers will be trained in assessing capacity by experienced mental health clinicians ([name]). A written consent form will need to be signed by the participant and a member of the research team in order to proceed with study participation. The participant will keep one copy and the research team will keep the original which will be scanned and uploaded to the electronic medical records. Participants will be given the option during the consent process to receive findings from the study, and permission will be sought to access medical records to retrieve clinical characteristics.

Research team members will assess each person's level of understanding during the recruitment and consent process, alongside discussion with patients' clinicians where necessary. Researchers will discuss the information sheet with patients and answer any questions they might have. If there are any doubts about the person's capacity to consent, this will need to be resolved before proceeding with study participation. If any doubts about their capacity emerge during the recruitment process, or capacity to consent appears to change during their participation, their capacity to consent will be re-evaluated before continuing with study participation.

If patients decline to participate, or withdraw their participation, this decision will be respected and patients are not required to give a reason for declining or withdrawing their participation. This decision will not have any impact on the patient's treatment or rights, and this will be made clear to patients on the information sheet and by researchers during the consent process.

6.3 Study assessments

Socio-demographic and clinical characteristics will be collected from all participants as part of the interview or from medical records. The survey will also include the following questionnaires:

- Social Contacts (SCA) ([name] et al. 2016)
- Time Use Survey (TUS) ([name] et al., 2016)
- Manchester Short Assessment of quality of life ([name] et al., 1999).

Participants will be asked using ad-hoc questions about their wishes to expand their networks; their willingness to do so with the help of professionals or carers or through internet tools; and their potential willingness to participate in a randomised controlled trial, if asked to. In further ad-hoc open questions, we will then ask for potential reasons for participating or not participating in a trial.

6.4 Withdrawal criteria

During the consent process, researchers will ensure that participants are aware of their right to decline participation at any stage of the research and that withdrawing participation will not affect their treatment or rights. Participants will be able to ask that their data is eliminated before the end of month 12 from the start of the project. If a participant wishes to withdraw from the study, researchers will record date of withdrawal and reason(s) for withdrawal.

7 STATISTICS AND DATA ANALYSIS

The analysis of the data will be discussed with the LEAP, which will have been established at the start of the programme and the LEAP members will help interpretation of the findings.

The number of screened participants, eligible participants and of those who refused participation or were not approached, and reasons for this where available will be recorded. The number and percentages of people who are willing and are not willing to participate in a future trial and of the reasons for this will be calculated. The distribution of the number of contacts in the sample and of the number of social activities reported by participants and the number of those willing to participate in a trial will be presented using descriptive statistics, including mean, median and standard deviation.

We wish to explore which socio-demographic (including social deprivation metrics and urbanicity) and clinical characteristics are associated with the number of social contacts and social activities, in order to identify patient characteristics (and potentially subgroups) which are associated with social isolation. Social deprivation and urbanicity metrics for each participant will be calculated from their LSOA codes bases on the data provided by the Office for National Statistics (English indices of deprivation 2015, Census 2011). We will examine the distributions of all sociodemographic and clinical characteristics and their correlation with each other. For any variables that are highly correlated with each other we will discuss and decide which variables to include in our modelling. We will exclude any binary variables where the prevalence is extreme and any variables with large numbers of missing values since these will not be useful in prediction. We will assess the presence of univariate associations between all remaining socio-demographic and clinical variables (including BPRS scores) and number of social contacts or social activities. Any variables that have a statistically significant relationship with social contacts or social activities univariately at the 10% level will be included in a multivariate model.

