7.2 Sample size calculation

Patients will be randomly selected for approach by clinicians or CSOs. The overall sample size will be 500 patients, which will give us a sufficiently robust estimate of later recruitment rates. If the rate of patients meeting the inclusion criteria and expressing a willingness to participate in a trial was 50%, we would estimate that with a confidence interval of 40% to 60%, i.e. with a margin of error of 10% which is sufficient for the given purpose.

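### Willingness among the 500 interviewed patients is conditional on having agreed to research, so it is likely to overstate the recruitment rate per eligible patient approached, and the stated interval does not cover this

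*Protocol*

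**What the plan says.** Objective 1 in the Study Summary assesses patients' wishes to expand their networks "in order to estimate recruitment rates for a future clinical trial". Section 7.2 of the protocol rests that estimate on the survey sample: "The overall sample size will be 500 patients, which will give us a sufficiently robust estimate of later recruitment rates". It illustrates the precision as follows: "If the rate of patients meeting the inclusion criteria and expressing a willingness to participate in a trial was 50"%, the estimate would come "with a confidence interval of 40% to 60%, i.e. with a margin of error of 10"%.

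The trial question is put in the interview, where participants are asked about "their potential willingness to participate in a randomised controlled trial, if asked to" (section 6.3). Before that, a patient must express interest to a clinician or answer a letter (6.1.1), meet a researcher and sign consent (6.2). On those who fall out, section 6.1.1 says: "If identified patients cannot be interviewed, we will approach other patients randomly selected from the list".

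Section 7 says that the numbers screened, eligible, refusing and not approached will be recorded, with reasons where available. The next sentence promises "The number and percentages of people who are willing and are not willing to participate in a future trial". It names no denominator, and nothing in section 7 or 7.2 connects the recorded counts to the recruitment rate.

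**The concern.** A recruitment rate for planning a trial is a rate per eligible patient approached. The survey observes willingness only in patients who have already agreed to one piece of research. Random selection for approach does not remove that condition, and neither does random replacement, because replacements pass through the same filters. Enlarging the sample narrows the interval around the conditional percentage without moving it towards the rate wanted.

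Section 7.2 calls the estimate sufficiently robust and allows only for sampling error. If the percentage among interviewees is carried into trial planning, the number of patients to approach and the time needed to recruit them are likely to be set too low. The hypothetical form of the question probably pushes the same way.

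**Working it through.** **Inputs from the protocol.** Sample n = 500 and illustrative rate p = 50% (7.2); stated interval 40% to 60% (7.2). The confidence level is not stated; 95% two-sided is assumed.

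**Inputs not given, so assumed over a range.** r = share of eligible approached patients who are interviewed (20% to 60%); k = willingness of non-participants relative to participants (0, 0.5 and 1).

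**Step 1: the plan's own figure.** Margin = 1.96 x sqrt(0.5 x 0.5 / 500) = 0.044, so the 95% interval is 45.6% to 54.4%. The stated 10-point margin is not reproduced: it needs only 1.96² x 0.25 / 0.10² = 96.04, that is 97 patients. That mismatch is a separate matter. It matters here because pure sampling error at n = 500 is small, so selection can easily be the larger error.

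**Step 2: rate per approached patient.**

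Rate = r x p + (1 - r) x k x p

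Overstatement = p - rate = (1 - r)(1 - k) x p = (1 - r)(1 - k) x 50 points

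| r | Approached to reach 500 interviews | k = 0 | k = 0.5 | k = 1 |
|---|---|---|---|---|
| 20% | 2,500 | 10% | 30% | 50% |
| 40% | 1,250 | 20% | 35% | 50% |
| 60% | 833 | 30% | 40% | 50% |

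Example: r = 0.4 and k = 0.5 gives 0.4 x 0.5 + 0.6 x 0.25 = 0.35.

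**Step 3: comparison with the error the plan allows for.** The overstatement exceeds the protocol's 10-point margin when (1 - r)(1 - k) > 0.2. That means r below 80% if k = 0, or r below 60% if k = 0.5.

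**Step 4: effect on the number to approach.** The factor is 50% divided by the rate per approached patient. Over r = 60% to 20% it is 50/30 = 1.67 to 50/10 = 5 if k = 0, and 50/40 = 1.25 to 50/30 = 1.67 if k = 0.5. If k = 1 it is 1.

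**Step 5: are the data there?** Eligible minus not approached gives the number approached. Approached minus refused minus interviewed gives the remainder (non-responders and unreachable patients). Section 7 plans to record each of these counts, so a rate per eligible approached patient can be computed without new data collection.

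**The case against.** The strongest reply is that section 7 names no denominator. It records the recruitment counts in the sentence just before the willingness percentage, and the choice of denominator and table layout could be left to a SAP that is not shown. This stands in part. A reader might infer that the protocol commits itself to the wrong denominator, and the text does not go that far. But section 7.2 does state that the 500 give a robust estimate of later recruitment rates, with no allowance for non-participation, and that statement is the protocol's own.

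Second, declining a survey is not declining a trial. The protocol says the survey offers participants no direct benefit, whereas the trial would test an intervention. Some patients who cannot be interviewed are also unavailable rather than unwilling: a patient hospitalised in the previous week is excluded but can be re-approached (5.2). This stands. A reader might infer that the rate is certain to be overstated, but if non-participants were as willing as participants there would be no bias, and if they were more willing the sign would reverse. At r = 40% the logical limits are 0.4 x 50 = 20% and 20 + 60 = 80%. Lower willingness among non-participants is the more plausible case, but it is not shown.

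Third, a reader might infer from section 7.2's joint condition (meeting the inclusion criteria and being willing) that the rate cannot be obtained from interviewees at all, since all of them meet the survey criteria. That holds only if the survey's criteria are meant. If the future trial's criteria are meant, the rate might be computable among the 500, depending on what those criteria are. The text is ambiguous, so this point supports a request for clarification and no more.

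**Conclusion.** The point holds as a likely, not a certain, overstatement. Followed as written, the estimate for objective 1 is conditional on having agreed to research, and the only uncertainty considered is sampling error. With 50% willing among interviewees and assumed participation of 20% to 60%, the rate per eligible approached patient is 10% to 30% if no non-participant would join, and 30% to 40% if non-participants are half as willing.

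A reader might take the 1.67 to 5 times understatement of patients to approach as the expected result. It is the extreme at k = 0; at k = 0.5 the factor is 1.25 to 1.67. Since the protocol gives neither r nor k, no single figure can be defended. What can be said is that over much of the plausible range the selection error exceeds both the 4.4-point sampling margin at n = 500 and the protocol's own 10 points. Nothing is lost if the rate is defined before analysis.

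**What to change.** In section 7, report two rates, each with a 95% confidence interval:

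- (a) willing / interviewed, labelled as conditional on survey participation;
- (b) willing / all eligible patients approached, keeping refusers, non-responders and replaced patients in the denominator, labelled as a lower bound on stated willingness, with refusals shown separately from patients who were unreachable or temporarily ineligible.

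In section 7.2, say that trial planning uses the range from (b) to (a), and whether the inclusion criteria in the rate are those of the survey or of the future trial. Rate (b) should not serve alone as the planning rate, because it counts unavailable patients as unwilling.

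The cost is some wording and one extra table from counts that the protocol already records. The downside is a less favourable and wider planning range. For example, with 1,250 approached and 250 of 500 interviewees willing, (a) is 50% and (b) is 250/1,250 = 20%.
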